## Co-Primary Outcome: Effectiveness (COVID-19 infection)

### Outcomes

New COVID-19 group home incidence (new laboratory-confirmed COVID-19 cases among residents, staff (together and then separately). Home-level COVID-19 infection incidence rates per 100 person-months were calculated by home and time period using the infection counts and follow-up time.

### Covariates

- *Study arm:* General Best Practice or Tailored Best Practice
- *Agency:* Unique identifier of the six provider organizations.
- *Group Home:* Unique identifier of the group home where resident lived or staff worked.
- *Stratification factors:* Stratification factors used for randomization, derived from the baseline racial and ethnic composition of group home residents and staff and a COVID-19 infection risk score.
- *Follow-up time (exposure):* Follow-up time in months for residents in a home was calculated using dates of residence based on intake and discharge data. Follow-up time for staff in a home was calculated using dates worked based on payroll data. Individual staff could contribute time to multiple homes during the same time period. Follow-up time for each home and follow-up period was calculated by totaling the resident and/or staff follow-up time in the home and period.
- *COVID-19 infection case count:* Resident and staff infection counts were determined to calculate incidence rate at the level of group home by time period. Multiple infections per-participant were counted if cases were at least 3 months apart. Resident infections were counted towards the home where they lived at time of infection. Staff often work in multiple homes concurrently. Since staff are being exposed to and/or exposing multiple home environments to infection, their case counts were allocated to any homes where they worked during the follow-up period they were infected.
- *Baseline incidence rate:* Home-level COVID-19 infection incidence rates per 100 person-

months were calculated by home and time period using the infection counts and follow-up time at baseline.

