We will employ a cluster-randomized trial design with 200 group homes randomized to the implementation of TBP compared to 200 group homes randomized to GBP. TBP consists of optimized, tailored, and highly specific COVID-19 best practices and training materials specific to the setting, staff, and residents with SMI and ID/DD in congregate living settings based on the comparative effectiveness of different types, intensities, and combinations of COVID-19 prevention practices (screening, isolation, contact tracing, use of PPP, vaccination) specifically modeled for residents and staff of congregate living settings for people with ID/DD and SMI derived by a simulation model. There are four main components to Tailored Best Practices: Measurement, Feedback, and House Plans; Motivational Interviewing; Interactive Education; and Trusted Messengers. Detailed descriptions of each component, along with supplemental materials, have been included in this submission in the attached TBP Manual [file name: "02_TBP Manual_2021NOV29_clean"]. In brief:

Measurement, Feedback, and House Plans:

Following each completion of the Fidelity survey (described below) by program directors (i.e., group home leaders) at baseline, 3-, 6-, 9, and 12-months post-randomization, the group home's program director will receive a statistical dashboard that shows the group home's fidelity performance in relation to other group homes. Visual, group home-level, easy-to-view displays will be provided, comparing current measures to prior measures and to the average performance and range of performance of other group homes in this study. The benchmarks also provide the opportunity for group home managers to discuss potential ways to improve and to potentially consult with "high performing" sites on strategies and lessons learned.

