Randomization will occur at the level of the group home stratified by group home type (SMI versus ID/DD), incident COVID-19 infection in the staff and residents (high incidence versus low incidence), and race/ethnicity (proportion non-Hispanic Caucasian versus other). TBP and GBP will be delivered within each agency as part of routine training activities. TBP sites will receive coaching to implement TBP specific to the setting, staff, and residents. Implementation fidelity will be measured including the proportion of staff and residents participating in recommended screening, isolating, contact tracing, PPP protocols, and vaccination interventions, along with the outcomes of new COVID-19 incidence as co-primary outcomes with group home as the unit of analysis. The outcomes will be assessed at baseline, 3, 6, 9, 12, and 15 months.

At each data collection point, we will evaluate implementation and effectiveness outcomes by secondary analysis of routine data collected by our community partners (e.g., dates of COVID-19 infection, hospitalization, mortality) as well as data from surveys completed by program directors (i.e., those who oversee individual group homes) assessing each group home's **fidelity and adoption** of their assigned set of best practices (TBP or GBP). These fidelity outcomes will be assessed at baseline, 3, 6, 9, 12, and 15 months.

We will also send the same fidelity survey to a second staff member at an equivalent level of the program director within the same group home (e.g., group home nurses). The purpose of this second fidelity survey will be to measure the intra-rater reliability of fidelity measures

[figure not shown]
within the same group home. If we have $\geq 80\%$ concordance between two raters in the first 10% of group homes surveyed, we will stop the second survey collection. If the concordance is $< 80\%$, we will continue to measure intra-rater reliability, using the same process above, until concordance is $\geq 80\%$ or until all group homes are surveyed again, whichever comes first. Re-training of TBP may occur between time points if concordance is $< 80\%$ and areas for improvement are identified by our research team.

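### The SAP charges one staff infection, unweighted, to every home worked in that follow-up period, including homes first worked after the test and homes in the other arm; this adds an avoidable, probably modest, dilution of the IRR

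*SAP*

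**What the plan says.** The SAP's Covariates section for the effectiveness outcome uses two attribution rules.

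- Residents: "Resident infections were counted towards the home where they lived at time of infection". This is one home, fixed by the infection date.
- Staff: "Staff often work in multiple homes concurrently", and because they may carry infection between homes, "their case counts were allocated to any homes where they worked during the follow-up period they were infected". This is every home in the period, with no weight stated.

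On staff person-time the same section says: "Follow-up time for staff in a home was calculated using dates worked based on payroll data". It adds: "Individual staff could contribute time to multiple homes during the same time period". It does not say whether a person's concurrent time is divided between homes or counted in full in each.

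The protocol (Research Design and Methods) has "200 group homes randomized to the implementation of TBP compared to 200 group homes randomized to GBP", with the home as the unit of randomisation, and states that "TBP and GBP will be delivered within each agency as part of routine training activities". Nothing in the text supplied confines a staff member to homes of one arm.

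The SAP's Analytical and Statistical Approaches section fits a Poisson mixed model with a home-level random intercept. It describes no de-duplication, no term for a case shared between homes, and no sensitivity analysis on attribution.

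**The concern.** The staff rule is looser than its own rationale. Shared exposure is a reason to share a case among homes worked around the time of infection. It is not a reason to charge a home the person had not yet entered. Because the rule follows the calendar period, a positive test on 2 October 2021 is charged to a home first worked in December 2021. It is not charged to a home the person left on 30 September, where exposure is more plausible. The last window runs from 1 April to 30 July 2022, four months, so the mismatch can reach further there.

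The rule can also enter one infection in both arms. A worker with one TBP home and one GBP home contributes a full case to each, whichever home was the source. That makes the arms look more alike than a single shared case would.

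Staff are about 3300 of the roughly 5500 people expected (1400 + 800 residents, 3300 staff). The rule touches the combined primary outcome, the staff analysis and, it appears, the baseline incidence covariate, which is built from the same counts.

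**Working it through.** **Inputs from the documents.** 200 homes per arm; about 3300 staff and 2200 residents (protocol). From SAP Table 1: staff 13.1% (GBP) and 6.8% (TBP); residents combined 26.5% and 17.8%; repeated-measures ICC 0.50; two-sided 0.05. Six time points (SAP, Time Frame).

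**The plan's own figure.** Treat homes as units with six repeated measures. The variance factor is (1 + 5 × 0.5)/6 = 0.583, so the effective n per arm is 200/0.583 = 342.9. A two-proportion test then has power 0.788 for staff and 0.785 for residents combined, close to the stated 80%. I use the Table 1 rates below only as a plausible true effect. I do not carry the dilution into power, because the planned test is a joint Wald test on treatment and treatment-by-time terms.

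**Assumptions, not in the documents.** A share s of staff work in exactly two homes with equal time in each; the two homes are allocated independently (1/4 both TBP, 1/4 both GBP, 1/2 mixed); mixed staff have the average of the two arm rates; staff and residents divide equally between arms.

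**Staff IRR.** With true ratio r = 6.8/13.1 = 0.519:

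- SAP rule, one full case per home: [(1 + s/2)r + s/2] / [(1 + s/2) + (s/2)r]
- Weights summing to 1: [(1 − s/4)r + s/4] / [(1 − s/4) + (s/4)r]

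At s = 0.3 these are (1.15 × 0.519 + 0.15)/(1.15 + 0.15 × 0.519) = 0.608 and (0.925 × 0.519 + 0.075)/(0.925 + 0.075 × 0.519) = 0.576.

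**Combined ratio.** Per arm, 1100 residents and 1650 staff. True: (1100 × 0.178 + 1650 × 0.068)/(1100 × 0.265 + 1650 × 0.131) = 308.0/507.65 = 0.607. At s = 0.3 the SAP rule gives (195.8 + 1650 × 0.09785)/(291.5 + 1650 × 0.16085) = 357.25/556.90 = 0.641. Weighting gives 315.80/499.85 = 0.632.

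| Share s | Staff IRR, SAP rule | Staff IRR, weighted | Combined, SAP rule | Combined, weighted | Counted/true staff cases, SAP rule |
|---|---|---|---|---|---|
| 0.10 | 0.553 | 0.538 | 0.619 | 0.615 | 1.1 |
| 0.20 | 0.583 | 0.557 | 0.631 | 0.623 | 1.2 |
| 0.30 | 0.608 | 0.576 | 0.641 | 0.632 | 1.3 |
| 0.40 | 0.631 | 0.596 | 0.652 | 0.640 | 1.4 |

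The unrounded combined differences are 0.004, 0.007, 0.010 and 0.012.

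**What drives the shift.** If no staff work across arms, the staff IRR stays at 0.519 under both rules, although the counts are still multiplied by 1 + s. Cross-arm work causes the dilution; count inflation by itself does not.

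**Wider sharing.** With three homes per multi-home worker and the other homes in the opposite arm half the time, the staff IRR is 0.670 (SAP rule) against 0.596 (weighted) at a 30% share, and 0.727 against 0.651 at 50%.

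**Standard errors.** I simulated 1000 trials with no true effect (400 homes, 3300 staff, two-home sharing) and compared arm totals by a simple Poisson test. With all duplicates inside one arm, it rejected 10.5% of the time at a 30% share and 13.7% at 50%, against a nominal 5%. With half the duplicates crossing arms, it rejected about 5%. This is not the SAP's mixed model, so the figures show direction only.

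**The case against.** The SAP states its rule openly and gives a reason. The outcome is incidence at home level, and no single home counts an infection twice; duplication appears only on summing across homes. The resident analyses do not use this rule and serve as a check. Most of the dilution is real contamination from randomising homes that share staff: at a 30% share, about 0.057 of the 0.089 shift in the staff IRR (0.519 to 0.576) remains after weighting, and only about 0.032 (0.576 to 0.608) comes from the counting rule. All of that stands, and it limits the size of the point. It does not justify charging homes first worked after the test.

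Three stronger inferences are tempting and are not supported.

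- *Inflated counts bias the IRR.* Inflation that is equal by arm cancels in the ratio.
- *Incidence rates are inflated.* That depends on whether concurrent staff time is split or counted in each home, which the SAP does not say. If it is counted in full in each, numerator and denominator broadly match.
- *Standard errors are too small throughout.* In the simulation this appeared when duplicates stayed within an arm, which is the case where the IRR is not diluted. The two harms belong to different patterns of staff sharing.

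It is also fair to say that the data descriptions list event dates and the homes worked in each three-month period, not shift dates by home. Payroll dates worked are mentioned only under person-time, so a short look-back may not be feasible.

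**Conclusion.** The point holds as a defect in the attribution rule with a probably modest effect. As written, the rule charges staff cases to homes worked only after the positive test and can place one infection in both arms, and nothing else in the SAP corrects for this. Under the two-home assumptions above, with 10% to 40% of staff sharing, the rule moves the staff IRR from 0.54–0.60 (weighted) to 0.55–0.63, and moves the combined ratio by about 0.004 to 0.012. The multi-home and cross-arm shares are not reported, so the true size is unknown. It would be larger if many staff work in three or more homes, and nil for the IRR if staff never cross arms. If TBP itself changed how many homes staff work in, the bias could go either way. The arithmetic does not isolate homes worked only after the test.

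A reader might infer that the primary effectiveness result is invalid. The documents do not support that. They support a cheap correction, plus disclosure of the shares that would settle the size.

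**What to change.** - Limit each staff case to homes worked on or before the positive-test date, within a fixed look-back if payroll detail allows. State which period receives the case when the look-back crosses a period boundary.
- Weight the case across those homes by payroll time share, with weights summing to 1.
- Split staff person-time between homes in the same way, and say so.
- Apply the same rule to the baseline incidence covariate.
- Use a robust or quasi-Poisson variance, since counts become fractional.
- Report the share of staff in more than one home and the share working across arms.
- Keep the current rule as a sensitivity analysis.

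The cost is reprogramming from payroll and test dates that the SAP already uses, and the inconvenience of fractional counts. No new data collection is needed unless the payroll extract lacks dates by home; in that case the look-back must be dropped or the detail requested from the provider organisations. Weighting will not remove the contamination from staff who truly work in both arms, and the report should say so.

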### Sample Size Calculations and Power

For power calculations we assumed a 2-tailed test with significance level .05, intraclass correlation (ICC) of 0.02 within the four randomization clusters (i.e., highest and lowest prevalence GHs within GBP and TBP), and ICC of 0.50 for repeated measures at the GH-level. Given COVID-19 incidence as of May 2020 rates based on available COVID-19 prevalence data for GHs residents and staff, we will have at least 80% power to detect 8.7 and 6.3% percentage point difference of COVID-19 infection between GBP and TBP for residents (ID/DD combined) and staff, respectively. We used conservative assumptions, given the possibility of undetected COVID-19 in GHs. The primary outcome is COVID-infections in both staff and residents with correction for type I error applying Bonferroni's method.

**Table 1.** Power calculations.

	Estimated COVID-19 Prevalence		Difference	Cohen's d a	Power
Population	Control (GBP)	Intervention (TBP)			
Group Home Staff	13.10%	6.80%	6.30%	0.38	80%
Residents with SMI & ID/DD combined	26.50%	17.80%	8.70%	0.28	80%
Residents with ID/DD	40%	30%	10%	0.24	80%
Residents with SMI	13.10%	6.80%	6.30%	0.38	80%

aSmall effect=0.2; Medium effect=0.5

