## Analytical and Statistical Approaches

The raw incidence rates were summarized across the homes by treatment group (Tailored Best Practices TBP vs Generic Best Practices GBP) for each time period. To compare the effectiveness between these groups, we fit a Poisson generalized linear mixed model with log-link for the group home level infection incidence rates over the 5 follow-up periods. The model included main effects for treatment group, linear and quadratic time trends over the follow-up periods, and interaction effects between treatment and the time periods. The model additionally included fixed effects for randomization factors, baseline incidence at each home, and group home agency, along with a group-home level random intercept.

A joint Wald test was performed to assess whether there were significant differences in the trends between treatment groups based on this model for the main effect for treatment including interactions between treatment and time trends. Estimates of the conditional incidence rate ratio (IRR) at each time point were calculated based on the linear combination of

the treatment main effect and treatment by time interaction effects. Correction for type I error was controlled by Bonferroni's method. Marginal mean incidence rates by treatment group per 100 person-months were estimated based on the model assuming 0 random effect. These analyses were repeated for various subgroups: staff, residents, IDD residents, and SMI residents separately. The analyses were performed in Stata 16.

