### [Changes to the Original Study Protocol](#)

We used an ANCOVA model in which outcomes observed at baseline were adjusted for as a covariate rather than included as a follow-up time point because of discrepancies in the definition of the fidelity score between the baseline and follow-up time points (resident masking was removed after baseline due to policy change). This approach was adopted for other endpoints to maintain consistency across all primary analyses. A quadratic term for time was included in the model to improve the model fit in accordance to observed trends.

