### Sample Size Calculations and Power

For power calculations we assumed a 2-tailed test with significance level .05, intraclass correlation (ICC) of 0.02 within the four randomization clusters (i.e., highest and lowest prevalence GHs within GBP and TBP), and ICC of 0.50 for repeated measures at the GH-level.

For the primary implementation outcome, the continuous Best Practices Fidelity score, we will have 80% power to detect minimum 0.21 standardized mean difference between intervention and control (Cohen's  $d = 0.21$ ). For a dichotomous fidelity threshold of 80% Best Practices Fidelity, we will have 80% power to detect 7.2% difference (Cohen's  $d = 0.33$ ).

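### The stated 80% power excludes the Bonferroni correction and is not for the joint test the SAP uses; the SMI-only and ID/DD-only rows appear to count all homes

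*SAP*

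**What the plan says.** For the effectiveness co-primary, the SAP (Sample Size Calculations and Power) states: "For power calculations we assumed a 2-tailed test with significance level .05, intraclass correlation (ICC) of 0.02 within the four randomization clusters". It adds an "ICC of 0.50 for repeated measures at the GH-level". Table 1 then gives 80% power in four rows: staff (13.1% v 6.8%), residents combined (26.5% v 17.8%), ID/DD residents (40% v 30%) and SMI residents (13.1% v 6.8%). The paragraph ends: "The primary outcome is COVID-infections in both staff and residents with correction for type I error applying Bonferroni's method". No n is shown for any row.

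The power section for the implementation co-primary uses the same level and ICCs: "we will have 80% power to detect minimum 0.21 standardized mean difference between intervention and control".

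The analysis sections describe a different test. For infection it is a joint Wald test "for the main effect for treatment including interactions between treatment and time trends", with linear and quadratic time, over five follow-up periods. Under Changes to the Original Study Protocol, "outcomes observed at baseline were adjusted for as a covariate rather than included as a follow-up time point". Both analysis sections mention Bonferroni again, without a divisor or a list of tests. On subgroups: "These analyses were repeated for various subgroups: staff, residents, IDD residents, and SMI residents separately".

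The protocol (Research Design and Methods) randomises 200 homes per arm, stratified by home type. It expects about 1400 SMI residents, 800 ID/DD residents and 3300 staff, and does not say how many homes are of each type.

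**The concern.** Power quoted at 0.05 describes the trial only if the test is run at 0.05. Here the paragraph that quotes 80% also says the level will be corrected, and the analysis section specifies a multi-parameter, baseline-adjusted test that the power section does not mention. A reader cannot tell at what level, or for which test, the 80% holds.

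The two single-type rows raise a separate question. SMI and ID/DD homes are distinct subsets of the 400, yet each row carries the same 80% as the all-home rows. If those rows were computed on all homes, a null SMI-only or ID/DD-only result would be read against power the subgroup did not have.

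**Working it through.** All figures are linear approximations to the planned models.

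**Inputs from the documents.** 200 homes per arm; six waves, five of them follow-ups; repeated-measures ICC 0.50; the Table 1 rates; fidelity d = 0.21; 1400 SMI residents, 800 ID/DD residents, 3300 staff.

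**Assumptions.** One unit per home and wave, unless people are counted; divisors 2, 4 and 5; an effect constant over time; homes split equally by type.

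**Step 1: units needed for 80% at 0.05.** n per arm = (z₁₋α/₂ + 0.842)² [p₁(1−p₁) + p₂(1−p₂)] / (p₁−p₂)², where (1.960 + 0.842)² = 7.849.
- Staff and SMI: 7.849 × 0.1772 / 0.063² = 350
- Combined: 7.849 × 0.3411 / 0.087² = 354
- ID/DD: 7.849 × 0.45 / 0.10² = 353
- Fidelity: 2 × 7.849 / 0.21² = 356

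The pooled-variance formula adds about 3, so the four rows need 350-356.

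**Step 2: units supplied.** Effective n per arm = 200 / [(1 + (m−1)0.5)/m]. With m = 6 this is 200 / 0.5833 = 343, which gives 78-79% in every row. The plan's 80% is therefore reproduced at uncorrected 0.05 on 1 df. The ICC of 0.02 is not needed. Treated as stratum variance removed by adjustment, it gives 200 × 6/3.38 = 355 units and about 80%.

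**Step 3: apply the correction.** At 0.025 the rows need 424-432 units. Without baseline adjustment the design cannot exceed 200/0.5 = 400, however many waves (417 in the 0.02 variant). On this basis 80% at the corrected level is out of reach. Detectable differences at 80% power, moving from 0.05 to 0.025:
- staff: 6.4 to 6.9 points (stated 6.3)
- combined residents: 8.8 to 9.6 points (stated 8.7)
- fidelity d: 0.214 to 0.235 (stated 0.21)

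**Step 4: the test actually used.** Treatment plus its interactions with linear and quadratic time gives 3 df on the natural reading. With five follow-ups and baseline correlation r, effective n = 200 / (0.6 − r²). At r = 0.50 (the plan's ICC) this is 571, with noncentrality 12.7-12.8. At r = 0.30 (a sensitivity value) it is 392, with noncentrality 8.7-8.8.

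| Two-sided level | Table 1 basis, 1 df | Adjusted joint test, r = 0.50 |
|---|---|---|
| 0.05 | 78-79% | 86% |
| 0.025 (divisor 2) | 69-70% | 79-80% |
| 0.0125 (divisor 4) | 60-61% | 71-72% |
| 0.01 (divisor 5) | 57-58% | 68-69% |

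At r = 0.30 the joint test has about 70% at 0.05 and 59-60% at 0.025.

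**Step 5: the single-type rows.** Step 1 shows that they imply the same n as the staff and combined rows. With half the homes and one unit per home and wave, 343/2 = 171 units give 49-50% at 0.05. With baseline adjustment at r = 0.50, 571/2 = 286 units give 71-72% on 1 df.

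Counting residents instead, effective n = 343 × share of homes × k / (1 + (k−1)ρ), where ρ is the within-home correlation and k = 1400/200 = 7 (SMI) or 800/200 = 4 (ID/DD). Unadjusted power at 0.05:

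| ρ | 0.10 | 0.20 | 0.30 | 0.40 | 0.50 |
|---|---|---|---|---|---|
| SMI | 98% | 94% | 87% | 80% | 74% |
| ID/DD | 93% | 87% | 81% | 75% | 69% |

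Both rows reach 80% up to ρ of about 0.31 at 0.05 and about 0.20 at 0.025. If SMI homes are 40-60% of the total, these limits range over 0.24-0.31 and 0.15-0.24.

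This does not explain the table as a whole. At ρ = 0.30 the combined row (k = 2200/400 = 5.5) has 802 units and the staff row (k = 3300/400 = 8.25) has 891, so each has about 99%. To give exactly 80%, ρ would have to be about 0.31 (ID/DD), 0.40 (SMI), 0.96 (combined) and 0.97 (staff).

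**The case against.** The best reply is that no sum in the plan is wrong. The SAP states 0.05 openly and 80% reproduces there. The loss from the correction belongs to an unadjusted six-wave analysis that the SAP does not run. With the plan's own ICC carried back to baseline, the adjusted joint test has 79-80% at 0.025, so a divisor of 2 would cost almost nothing against the stated figure. An adjusted 1-df contrast would have about 90%. This largely stands for the all-home rows, but it depends on a correlation and a divisor the SAP does not give, and the 90% is for a contrast other than the joint test.

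The value 0.30 is a sensitivity choice. The SAP's own reason to expect a weaker baseline correlation, "discrepancies in the definition of the fidelity score between the baseline and follow-up time points", concerns fidelity only and says nothing about infection. That limit is accepted.

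The Bonferroni scope is also unclear. In the infection analysis section the sentence follows the time-point rate ratios and might cover only those. But the power section ties it to the primary outcome, so the ambiguity is itself part of the problem.

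For the single-type rows, 80% could be a floor: the text above Table 1 says at least 80% for combined residents and staff. Counting people once with a within-home ICC of 0.02 gives ID/DD 82%, SMI 96% and the others above 99%. This reading cannot be excluded. It sits badly with the protocol's choice of the home as unit of analysis, with the SAP attaching 0.02 to randomisation clusters, and with four rows of nearly identical implied n.

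Finally, the SAP reports completed fits. Restated power cannot change the design, and a null subgroup result is better judged by its confidence interval. That limits the consequence but does not make the stated 80% interpretable.

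**Conclusion.** The concern holds, with medium confidence, and should be corrected.

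- **Correction.** On the basis that reproduces Table 1 and the fidelity figure, the 80% excludes Bonferroni. A divisor of 2 costs about 9 points and a divisor of 4 about 18.
- **Test.** The available SAP text states no power for the baseline-adjusted joint test. It may be close to 80% at 0.025 if the baseline correlation is 0.50, and is about 20 points lower at 0.30.
- **Single-type rows.** That they were computed on all homes is an inference from the equal implied n. 80% is attainable for both if residents are counted individually and the within-home correlation is no more than about 0.3, but the SAP does not state that correlation.

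These conclusions rest on the assumed divisors, a constant effect, an equal split of homes and the linear approximation. The opening of the SAP was not available, so statements about omissions apply to the rest of it.

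**What to change.** - State the Bonferroni divisor and the tests it covers: staff and residents, the two co-primaries, the time-point contrasts, or some combination.
- At that level, restate power and detectable differences for the baseline-adjusted joint test over five follow-ups. Make the baseline correlation explicit: 0.50 from the stated ICC, plus a lower sensitivity value such as 0.30.
- Give the number of homes and people behind each Table 1 row. Recompute the SMI-only and ID/DD-only rows on their own numbers with the within-home correlation stated, or mark them as not separately powered.
- Use planning inputs, not observed results, and leave the test unchanged. Because the SAP already reports fitted models, label the new figures as added later.

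The cost is one recalculated table and a few sentences, with no additional homes. The drawback is that some power figures, mainly for the single-type rows, may look less favourable.
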